3. STUDY OBJECTIVES AND ENDPOINTS

The main objective of this roll-over study is to provide continued access to S95014 during the consolidation phase in patients who completed the CL2-95014-002 study and who are clinically benefitting from S95014 without major toxicity.

Secondary objective of this roll-over study is to assess the safety profile of lyophilized S95014 during the consolidation phase. All adverse events regardless of grade or causality and severity will be collected after the informed consent is signed and during the entire treatment period (see [section 8](#)).

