Biochemistry	Albumin, Alkaline Phosphatase (ALP), ALT, AST, Ammonia, Bicarbonates, Gamma-glutamyl-transferase (GGT), Lactate dehydrogenase (LDH), Calcium, Phosphorus, Sodium, Potassium, Creatinine, Total Bilirubin, Total Cholesterol, LDL, HDL, Triglycerides, BUN or Urea, Uric Acid, Amylase, Lipase, Glucose
Urinary analysis	Macroscopic Panel (Dipstick) (Blood, Glucose, Ketones, Protein) If the dipstick test is at least 2+ on one or more parameter(s), quantitative urinary biochemistry tests will be performed on the abnormal parameter(s)
Blood coagulation	Prothrombin time - International Normalized Ratio (INR), fibrinogen, protein S activity, antithrombin activity, activated Partial Thromboplastin Time (aPTT), D-dimer, FDP
Hepatitis serology	HbsAg, HbsAb, HbcAb, if HbsAg or HbcAb positive check viral load (HBV-DNA) at baseline, HCV RNA-PCR, HEV RNA-PCR
Pregnancy Test	Pregnancy testing is mandatory at inclusion (serum), before each phase of the consolidation (i.e. S1, S2, S3) and at withdrawal visit (serum) for WOCBP

All samplings for biochemistry should be taken in fasting conditions.

Abnormal laboratory values or test/exams results (i.e. blood pressure recording) will constitute an AE if they are:

- associated with signs and symptoms, or
- deemed clinically significant in the investigator's opinion, or
- if they require curative therapies, or
- associated with delay of study medication, or
- associated with study discontinuation

Triplet ECG will be assessed at inclusion and at the withdrawal visit.

LVEF assessment will be performed through echocardiography or MUGA scan at inclusion and at the withdrawal visit.

Results of LVEF assessment and ECG performed in the frame of previous CL2-95014-002 study withdrawal visit can be used to assess patient's inclusion in order to avoid unnecessary exam

Post-withdrawal follow-up: After the withdrawal visit, a contact or telephone call will be done approximately 30 days after the last S95014 infusion, except in case of consent withdrawal. The following information will be collected:

- follow-up adverse events
- the first new anticancer treatment after withdrawal and its starting date.

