8.3. Definition of Adverse events

An adverse event is defined as any untoward medical occurrence in a subject participating in a clinical study, whether or not there is a causal relationship with the IMP and/or experimental procedures, occurring or detected from the date the participant signs the information and consent form, irrespective of the period of the study (periods without administration of the IMP (e.g. run-in period) are also concerned).

An adverse event can therefore be:

- any unfavourable and unintended sign (including an abnormal finding from an additional examination such as lab tests, X-rays, ECG, ...) which is deemed clinically relevant by the investigator,
- any symptom or disease,
- any worsening during the study of a symptom or a disease already present when the participant entered the study (increase in frequency and/or intensity), including the studied pathology,

and detected during a study visit or at an additional examination or occurred since the previous study visit (including relevant event reported in participant's diary or safety evaluation scale).

Of note:

Any hospitalisation for administration of anti-tumoral treatment and/or associated protocol (during or after the study) or other care measures for cancer (e.g. overnight hospital stay to receive a blood or platelets transfusion), for social reasons, educational purpose (e.g. learning of diabetes management by the participant) or routine check-up should not be considered as an adverse event and should not be reported in the e-CRF. The following procedures, whether planned before the study or not, whether leading to a hospitalisation or not, **should not be reported in the e-CRF and kept in the source data (or patient file):**

- therapeutic procedures related to a non-aggravated medical history (e.g. cataract extraction not due to an aggravation of the cataract during the study, haemodialysis sessions related to a renal insufficiency not aggravated during the study),
- prophylactic procedures (e.g. sterilisation, wisdom teeth removal),
- comfort procedures (e.g. cosmetic surgery),
- control procedures of a pre-existing condition without aggravation (e.g. colonoscopy to control the remission of colon cancer).

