8.9. Reporting procedures

8.9.1. Time frame for AE reporting

Any event meeting the above mentioned definitions (see sections 8.3 to 8.7) must be reported to the sponsor on an adverse event form if it occurred:

- before the first intake of the IMP for events related to the research
- at any time after the administration of IMP, up to the participant's withdrawal visit for all events,
- up to 30 calendar days after the participant's last intake of IMP for all ERIN, regardless of the supposed role of the research.
- irrespective of the time of onset after the end of the study in case of serious adverse event related to the research.

[figure not shown]
Of note, events occurring between the signature of the informed consent and the first administration of the test drug for which the investigator does not consider an association with

¹ Instrumental Activities of Daily Living (ADL) refer to preparing meals, shopping for groceries or clothes, using the telephone, managing money, etc.

² Self-care ADL refer to bathing, dressing and undressing, feeding self, using the toilet, taking medications, and not bedridden”.

any procedure/condition required by the study protocol must be reported as **medical history** or as signs and symptoms related to the studied disease in the dedicated form of the CRF.

For a given patient, medical histories and adverse events already reported in the initial CL2-95014-002 study will not be reported in the eCRF, except in case of worsening.

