8.9.2.4. Recording Methods in the e-CRF

Adverse events must be documented on the « Adverse Event » page of the e-CRF.

In case of chronic disease:

- if the disease is known when the participant enters in the study, only worsening (increased frequency and/or intensity of the episodes/attacks) will be documented as an adverse event,
- if the disease is detected during the study and if repeated episodes enable diagnosis of a chronic disease, the episodes will be grouped on the «Adverse Event» page previously created for the event which will clearly describe the diagnosis.

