3.3.3. Demographic data and other baseline characteristics

Demographic and baseline measurements will be summarized for the SAS, using standard descriptive summaries or categorical summaries, as appropriate. In addition to the summary tables, a listing will be provided for all demographic and baseline characteristics data.

In addition, listing of medical history will be provided. For this purpose, data of the CL2-95014-002 study may be used.

The following baseline characteristics will be summarized based on descriptive statistics:

- Age at inclusion (years; if not available, then it will be calculated as the biggest integer $\leq [(ICF\ date - date\ of\ birth + 1) / 365.25]$)
 - As continuous variable
 - By Age Category I (age <10, 10 - <16, and ≥ 16 years)
 - By Age Category II, EudraCT categories (0-27 days, 27 days-23 months, 2-11 years, 12-17 years, 18-65 years, ≥ 66 years)
- Sex
- Race
- Ethnicity
- Height (cm)
- Weight (kg)
- Body Mass Index (BMI (kg/m²) = weight (kg) / height (m²))
- Body Surface Area (BSA(m²) = sqrt (height (cm) x weight (kg) / 3600))

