3.5.1. Adverse Events

A treatment-emergent adverse event (TEAE) is defined as any untoward medical occurrence in a subject who received IMP (S95014), which occurs within the period from the Inclusion visit, until 30 days after the last S95014 infusion, or the date of withdrawal, whichever is earlier. TEAE will be assessed according to the National Cancer Institute (NCI) Common Terminology Criteria Adverse Events (CTCAE) v5.0. Clinically significant laboratory abnormalities will be classified into Common Terminology Criteria (CTC) grade according to CTCAE v5.0 and will be reported as adverse events if they are associated with signs and symptoms or, clinically significant in the investigator's opinion except if related to the disease, if they require curative therapies, if they induce change of study treatment administration. All analyses described below will be based on TEAEs, if not otherwise specified.

Adverse events will be summarized in hierarchical tables, presenting the number and percentage of subjects having at least one AE, and having at least one AE in each primary system organ class and for each preferred term using MedDRA coding. AEs will be sorted by descending frequency, and alphabetically where frequency is tied. Such summaries will be produced for all AEs, serious adverse events (SAEs), grades 3 or 4 AEs, AEs leading to study treatment discontinuation, and AEs leading to dose-adjustment or interruption of any of the drugs of the treatment. All of these summaries will be by system organ class, preferred term, starting dose level if applicable and, in some case, worst grade. Most of the summaries will be produced twice, once for all events regardless of study treatment relationship, and once for events suspected to be study treatment related. All deaths will be listed and summarized. All AEs will be listed, and any other information collected (e.g., start/end dates and duration of adverse event, severity or relatedness to study medication) will be listed as appropriate.

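### Protocol 8.9.1 leaves an unchanged, ongoing CL2-95014-002 event without an AE record here even if it leads to S95014 being held or stopped, so the SAP 3.5.1 discontinuation and interruption tables can be incomplete

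*Protocol*

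**What the plan says.** Protocol 8.9.1 sets the reporting window. Once S95014 has been given, events are reportable "at any time after the administration of IMP, up to the participant's withdrawal visit for all events". The section closes with a roll-over rule for medical histories and adverse events: "adverse events already reported in the initial CL2-95014-002 study will not be reported in the eCRF, except in case of worsening".

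Other sections bear on the same events:

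- **Protocol 3** states the scope without that limit: "All adverse events regardless of grade or causality and severity will be collected after the informed consent is signed".
- **Protocol 8.3** defines worsening through frequency as well as intensity. An adverse event includes "any worsening during the study of a symptom or a disease already present when the participant entered the study (increase in frequency and/or intensity"). Section 8.9.2.4 repeats this for chronic disease known at entry: "only worsening (increased frequency and/or intensity of the episodes/attacks) will be documented as an adverse event".
- **Protocol 8.2** makes an abnormal result an adverse event on any one of several grounds. Two of them are a delay of study medication and being "associated with study discontinuation". Neither requires worsening.
- **SAP 3.5.1** plans summaries of "AEs leading to study treatment discontinuation, and AEs leading to dose-adjustment or interruption", based on treatment-emergent events unless otherwise specified.
- **SAP 3.3.3** mentions data from the earlier study only for baseline and history: "In addition, listing of medical history will be provided. For this purpose, data of the CL2-95014-002 study may be used".

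**The concern.** Safety is the only outcome analysed in this study; Protocol 7 marks efficacy as not applicable. Every child has already had S95014 in CL2-95014-002, so some may enter with an induction event that has not fully resolved. If such an event persists unchanged and S95014 is then held or stopped because of it, this study has an action on treatment but, under 8.9.1, no event to attach it to.

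The tables of events leading to discontinuation or interruption are where a reader looks for tolerability over nine planned infusions. An omission there loses the event term, grade, causality and outcome. It also leaves the report inconsistent with itself: a child can be counted under adverse events as the reason for stopping in the disposition table and be absent from the adverse event table for discontinuation.

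**Working it through.** The plan gives no figure to reproduce on this point, so the check sets the rules side by side. A short calculation then gives the scale.

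**Test case.** An adverse event reported in CL2-95014-002 is ongoing at inclusion, does not increase in frequency or intensity, and leads to S95014 being interrupted or stopped.

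| Place | What it implies for the test case |
|---|---|
| Protocol 8.9.1 | Not entered in this eCRF, because worsening is the only exception |
| Protocol 3 | All adverse events after consent are collected; no exception for the earlier study |
| Protocol 8.2 | If it is an abnormal result tied to a delay or a stop, it is an adverse event |
| Protocol 5.6.2 | If it causes premature withdrawal, its outcome goes in the adverse event part of the eCRF |
| Protocol 8.9.2.2 | A change in the measures taken goes on the page already created; which study's page is not said |
| Protocol 6.3 | Prior treatments are left out only if no longer ongoing; the adverse event rule has no such limit |
| Protocol 17.1.3 | Data from CL2-95014-002 could be used in the report; optional, with no merging rule |
| SAP 3.5.1 | A treatment-emergent event must occur from the inclusion visit onward; an earlier onset is not clearly covered |

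**Can the test case arise?** Yes. Protocol 5.6.1 allows a stop for an adverse event on the investigator's judgement. Several rows of the table in Protocol 8.10 act on lack of recovery rather than on worsening. Non-inclusion criteria 9 and 13 remove significant laboratory abnormalities judged to endanger the child and major safety issues from earlier S95014. Lesser unresolved events remain eligible.

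**Does the SAP repair the gap?** No. It has no rule for bringing adverse events across from CL2-95014-002. Even if a site did enter the event, its onset before inclusion leaves its place in the tables unclear.

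**Where does the action still show?** SAP 3.3.1 tabulates discontinuation by primary reason, and SAP 3.4.1 lists dose changes and interruptions with reasons. For laboratory toxicity, the shift tables in SAP 3.5.2 use the baseline of SAP 3.1.2, the last usable value before the first dose in CL2-95014-002. A persisting laboratory abnormality would therefore appear there.

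**Scale.** Input: about 88 planned children (Protocol synopsis), all assumed to be treated. The shift from k omitted children is 100 × k / 88 percentage points.

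- k = 1: 100 / 88 = 1.14
- k = 3: 300 / 88 = 3.41
- k = 5: 500 / 88 = 5.68

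The values of k are illustrative. If a table wrongly showed 0 of 88, its one-sided 95% upper limit would be 1 − 0.05^(1/88) = 3.3%. In the tables by starting dose the denominator is smaller, so each omission weighs more; the group sizes are not given.

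**The case against.** The closing sentence of 8.9.1 has a sensible purpose: it avoids entering the same event in two linked databases. Other sections already capture much of what matters. Protocol 5.6.2 covers outcome when an event causes withdrawal, 8.2 covers abnormal results tied to a delay or stop, and 8.1 asks that any significant abnormality found from consent to the withdrawal visit go on the appropriate eCRF page. Criteria 9 and 13 narrow the group, and criterion 13 names non-recovery of safety parameters as an example. The stop or hold stays visible in the disposition table and the dose-change listing.

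This limits the point but does not remove it. None of these sections says that it overrides 8.9.1, and 8.9.2.2 leaves open which study's record is updated. The disposition table and the dose-change listing show that treatment changed and why in brief. They do not supply grade, causality and outcome. The gap is clearest for a non-laboratory event that leads to a hold, because neither 5.6.2 nor 8.2 reaches it.

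A reader might infer more: that 8.9.1 also bars an event that resolved after induction and returns at the same or a lower grade on re-exposure. The documents do not support that. A new episode after dosing falls within the general duty in 8.9.1 to report all events up to the withdrawal visit, and worsening in 8.3 and 8.9.2.4 includes increased frequency. What remains is an ambiguity. The frequency wording concerns conditions present or known at entry, so a site could misread the rule for an event that had cleared.

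**Conclusion.** The point holds for events that are ongoing and unchanged at roll-over. Protocol 8.9.1 conflicts with 3, 5.6.2 and 8.2, and it is out of step with 6.3. If sites follow it literally, the SAP 3.5.1 tables of events leading to discontinuation or interruption can be incomplete and can disagree with SAP 3.3.1 and 3.4.1. It should be corrected, since those tables serve the study's only analysed objective.

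The number of children affected cannot be derived, because the documents give no rates of unresolved induction events. The size is stated only per child: about 1.1 percentage points if all 88 are treated.

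Two stronger conclusions do not follow. Treatment-emergent incidence is not shown to be understated: an unchanged event with onset before inclusion would properly stay out of those counts. Nor can lost recurrences be estimated by applying assumed rates to 88 children. Recurrence is reportable on the plain reading, neither rate is in the documents, and such a product would also assume that every site omits every recurrence.

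**What to change.** Reconcile Protocol 3, 5.6.2, 8.2, 8.9.1 and 8.9.2.2 by amending the closing sentence of 8.9.1 so that:

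1. A new episode after recovery is a new adverse event in this study, at any grade.
2. Any CL2-95014-002 adverse event ongoing at inclusion is entered once in this eCRF, with its original onset date and its grade at inclusion, and flagged as ongoing from that study. Action taken on S95014 and outcome are recorded on that page.
3. A flagged event stays out of the treatment-emergent counts unless it worsens in frequency or intensity, as 8.3 defines it. A test on grade alone would be narrower than the protocol's own definition.

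In SAP 3.5.1, state how flagged events stand under the treatment-emergent definition. Show those that lead to interruption or discontinuation on a separate line of the two tables, so that they can be checked against the disposition table and the dose-change listing.

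The cost is one amended protocol sentence, one eCRF flag, one extra line in two tables and a little more data entry at inclusion. The change concerns data capture and display only; no clinical stopping rule is altered.

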8.9.2. Responsibilities of the investigator

For any adverse event and special situation mentioned above the investigator must:

- **Note in the participant's medical file** the date on which he/she learned of the event (at a follow-up visit or a telephone contact with the participant or a third person, ...) and any other relevant information which he/she has learned of the event,
- **Assess** the event in terms of seriousness, intensity and causality,
- **Report the event to the sponsor** using the AE form (in case of ERIN, the reporting should be done immediately),
- **Document** the event with additional useful information,
- Ensure the **follow-up** of the event,
- **Fulfil his/her regulatory obligations** to the Competent Authorities and/or to the IEC, in accordance with local regulations.

Moreover, the investigator must report to the sponsor and/or to the IEC and/or to the Competent Authorities in accordance with the local regulation, any new information that might materially influence the benefit-risk assessment of the test drug or that would be sufficient to consider changes in the test drug administration or in the overall conduct of the clinical investigation.

8.9.2.1. Documentation of the event

The investigator must ensure that all events are well documented. In particular for ERIN, he/she should provide the sponsor, as they become available, with anonymized copies of the documents which provide additional useful information, such as hospital admission reports, reports of further consultations, laboratory test reports, reports of other examinations aiding diagnosis (where possible, the results from pre-test drug assessments should be appended for comparison with the results obtained under test drug), or the autopsy report, if autopsy is performed.

8.9.2.2. Follow-up of adverse events

The investigator must ensure that follow-up of the participant is appropriate to the nature of the event, and that it continues until resolution if deemed necessary.

Any change in terms of diagnosis, intensity, seriousness, measures taken, causality or outcome regarding an adverse event already reported must be written up in a new complete evaluation of the event documented on an “Adverse event” page previously created for the event.

If the adverse event has not resolved at the participant's final visit in the study, the participant must be followed up suitably and any information on the outcome of the event will be noted on an « Adverse Event » page previously created for the event

If the follow-up of the participant is not done by the investigator him/herself (hospitalisation, followed by a specialist or the participant's general practitioner, ...), the investigator will do everything to establish/maintain contact with the person/department in charge of follow-up of the participant.

8.9.2.3. Special situations (pregnancy, overdoses, intake of IMP/NIMP a person around the participant)

Pregnancy

If a female participant in the study becomes pregnant, the investigator must:

- stop immediately the test drug (if the pregnancy is a non-inclusion criterion),
- report it on an « Adverse Event » page as well as on the specific paper pregnancy form (1st page) to be notified immediately (ERIN),
- contribute to the follow-up of this pregnancy and provide the sponsor with information concerning this follow-up (notably using the 2nd page of the specific paper pregnancy form).
- If the partner of a participant becomes pregnant during the course of the study, the pregnancy should not be reported in the e-CRF. The investigator should **immediately** contact the sponsor (contact details provided in the investigator's study file) who will inform him/her about the procedure to be followed.

Overdose of IMP or NIMP

- In case of overdose, the investigator should report it on an “Adverse Event” page to be notified immediately (ERIN).

- Overdose should be followed-up to ensure that the information is as complete as possible with regards to:
 - o dose details (number of units, duration...) and, if multiple overdose, details regarding other medicinal products or substance,
 - o context of occurrence, i.e. intentional (suicide attempt, other reason) or accidental (error in prescription, administration, dispensing, dosage),
 - o related signs and symptoms ("No related adverse events" to be reported otherwise),
 - o outcome.
- Insofar as possible, a blood sample should be collected for assay of the IMP taken.

Intake of IMP/NIMP by a person around the participant

This event should not be reported in the e-CRF. The investigator should immediately contact the sponsor (contact details provided in the investigator's study file) who will inform him/her about the procedure to be followed.

